1.1. Objectives and Endpoints

1.1.1. Objectives

Primary objective

The primary objective of the study is to demonstrate that Super-Responders (SRe; defined as psoriasis subjects who receive on-label guselkumab treatment until week 20 and respond with a Psoriasis Area and Severity Index [PASI] score = 0 at weeks 20 and 28) maintain control of disease until week 68 with prolonged treatment intervals of 16 weeks (100 mg q16w). *To be demonstrated in Study Part 2.*

Secondary objectives

Secondary objectives are to evaluate

- whether subjects with short disease duration (≤ 2 years) show a more rapid and better guselkumab response compared to subjects with longer disease duration and whether subjects with shorter disease are more likely to maintain drug-free control of disease after guselkumab withdrawal. *To be evaluated in Study Parts 1, 2 and 3.*
- whether SRe with short disease duration and PASI=0 at week 116 (ie, remission for one year after withdrawal) will show sustained remission (ie, PASI=0) over two additional years compared to subjects with longer disease duration. *To be evaluated in Study Part 3.*
- whether SRe with short disease duration and PASI>0 to ≤ 5 at week 116 (ie, partial relapse for one year after withdrawal) will show continued loss of response or stabilization of disease worsening over two additional years compared to subjects with longer disease duration. *To be evaluated in Study Part 3.*
- whether different treatment intervals (weeks 28 to 60: guselkumab 100 mg q8w vs. guselkumab 100 mg q16w) affect the maintenance of drug-free control of disease after 68 weeks of guselkumab treatment. *To be evaluated in Study Part 3.*
- the safety and tolerability of guselkumab in subjects with moderate-to-severe plaque-type psoriasis.

Note: Disease duration will be calculated from date at which first symptoms (plaque) were reported by subject to date of screening visit:

- Disease duration (days) = Date of visit 1 – date of first symptoms +1.

Exploratory objectives

The exploratory objectives are to be explored in the mechanistic biomarker substudies. These objectives are out of scope of this SAP.

1.1.2. Endpoints

For the endpoints, the following terms were defined:

- Control of disease: PASI score <3
- Fluctuating disease: PASI score 3 to 5
- Loss of disease control: PASI score >5.

Study groups are defined as follows:

- **1:** All participating subjects who are enrolled and are scheduled to receive guselkumab 100 mg at weeks 0, 4, q8w until week 28 (*Study Part 1*)
- **2a:** SRe (PASI score = 0 at weeks 20 and 28) randomized to guselkumab 100 mg q8w at weeks 28 to 60 (*Study Part 2*)
- **2b:** SRe randomized to guselkumab 100 mg q16w at weeks 28 to 60 (*Study Part 2*)
- **2c:** non-SRe with a PASI score >0 at week 20 and/or 28 who will receive guselkumab 100 mg q8w at weeks 28 to 60 (*Study Part 2*)
- **2d:** SRe with loss of disease control between week 28 and 68, who will enter the re-treatment arm and receive guselkumab 100 mg at weeks 0, 8 and 16 calculated from the date of loss of disease control (*Study Part 2*)
- **3a:** SRe randomized to guselkumab 100 mg q8w in *Study Part 2* with withdrawal of guselkumab at week 68 (*Study Part 3*)
- **3b:** SRe randomized to guselkumab 100 mg q16w in *Study Part 2* with withdrawal of guselkumab at week 68 (*Study Part 3*)
- **3c:** SRe with fluctuating disease at week 68 or loss of disease control at any other visit after week 68, who will enter the re-treatment arm and receive guselkumab 100 mg at weeks 0, 8 and 16 calculated from the date of loss of disease control (*Study Part 3*).

Primary endpoint

The primary endpoint of the main study is the proportion of subjects in study groups **2a** and **2b** who achieve an absolute PASI score <3 at week 68.

Major secondary endpoints

Major secondary endpoints of this study are:

- Time to improvement from baseline (week 0) in PASI (PASI 75/90/100 response and absolute PASI score=0) for subjects with short (≤ 2 years) and longer (>2 years) disease duration per study group (**1, 2a, 2b, and 2c**)
- Proportion of subjects with short (≤ 2 years) and longer (>2 years) disease duration who achieve an absolute PASI score of 0, ≤ 1 and <3 at weeks 20, 28, 68, 116, 164, and 220 per study group (**1, 2a, 2b, 2c, 3a, and 3b**)
- Proportion of subjects who retain disease control (ie, absolute PASI score <3 at all visits) from week 68 through week 116, from week 68 through week 164, and from week 68 through week 220 for subjects with short (≤ 2 years) and longer (>2 years) disease duration per study group (**3a and 3b**).

Other secondary endpoints of this study are:

- Proportion of subjects who achieve a PASI 75/90/100 response at weeks 20, 28, 68, 116, 164, and 220 per study group (**1, 2a, 2b, 2c, 3a, and 3b**)
- Time to loss of disease control (absolute PASI score >5 at any visit) after treatment withdrawal beyond week 68 per study group (**3a and 3b**)
- Proportion of subjects with an absolute PASI score=0 at all of the following visits: weeks 12, 16, 20, and 28 (**study group 1**)
- Change from baseline (week 0) in Dermatology Life Quality Index (DLQI) score at weeks 28, 68, 116, 164, and 220 per study group (**1, 2a, 2b, 2c, 3a, 3b, and 3c**)
- Proportion of subjects who achieve a DLQI score 0/1 and <5 at weeks 28, 68, 116, 164, and 220 per study group (**1, 2a, 2b, 2c, 3a, 3b, and 3c**)
- Change from baseline (week 0) in affected Body Surface Area (BSA) at weeks 12, 28, 52, 68, 80, 104, 116, 140, 164, 188, 212, and 220 (**all study groups**)
- Change from baseline (week 0) in the Nail Assessment in Psoriasis and Psoriatic Arthritis (NAPPA) score at weeks 28, 68, 116, 164, and 220 among subjects with nail psoriasis at baseline (week 0; **1, 2a, 2b, 2c, 3a, and 3b**)
- Change from baseline (week 0) in the signs and symptoms aggregate scores of the Psoriasis Symptoms and Signs Diary (PSSD) at weeks 28, 68, 116, 164, and 220 (**1, 2a, 2b, 2c, 3a and 3b**)
- Proportion of subjects who achieve a PSSD sign score=0 at week 68 among subjects with a PSSD sign score ≥ 1 at week 28 per study group (**2a, 2b, and 2c**)
- Association between trough serum guselkumab concentration and efficacy or serum biomarker level
- Association between trough serum guselkumab levels at weeks 20, 28, 36, and 68 and achieving a PASI score <3 at week 68 per study group (**2a and 2b**)
- Proportion of subjects who were re-treated due to loss of disease control (PASI >5) and regain control of disease (PASI <3) 24 weeks after start of re-treatment (study groups **2d and 3c**)
- Safety and tolerability with regard to adverse events (AEs) and abnormal laboratory results (**all study groups**).

1.2. Study Design

The present trial is designed as a phase 3b, randomized, double-blind, parallel-group, multicenter, comparison study in subjects of at least 18 years of age with moderate to severe plaque-type psoriasis. The study features the following structure and design:

Study Part 1: Screening through Week 28:

Part 1 consists of a screening phase lasting up to four weeks (+ 7 calendar days) prior to first administration of guselkumab (week 0), followed by a 28-week run-in period with visits and administration of 100 mg guselkumab at weeks 4, 12, and 20. In case of a PASI score = 0 at weeks 20 **and** 28, subjects are qualified to be randomized either to study group **2a** or **2b** of Study Part 2. In case of PASI score >0 at weeks 20 and/or 28, the subjects continue to receive guselkumab

100 mg q8w until week 60 (last administration at week 60 visit) with final study assessments at week 68 and final safety follow-up visit at week 72 (defined as study group **2c**).

Study Part 2: Week 28 through Week 68:

Subjects with a PASI score = 0 at weeks 20 **and** 28 are defined as SRe and randomly assigned to the following two treatment groups: **2a**) guselkumab 100 mg q8w or **2b**) guselkumab 100 mg q16w. In addition, subjects with disease duration \leq 2 years are equally distributed to either group by stratified randomization. Study visits of Study Part 2 are conducted every 8 weeks.

To blind the study, study treatment (guselkumab or Placebo) is administered q8w starting at week 28 until the end of study therapy (last administration in week 60). The q16w group receives Placebo at weeks 28, 44 and 60. Subjects losing control of disease, defined as PASI score >5 at any visit during Study Part 2 (ie, until week 60), enter the Re-treatment arm (group **2d**, see section Re-treatment below).

The assessment for the primary endpoint is made at week 68 for both study groups (**2a** and **2b**).

In case of PASI <3 at week 68, the subject does not receive any study medication and enters the drug withdrawal part (Study Part 3). In case of PASI ≥ 3 at visit week 68 the subject enters the re-treatment arm **3c** (see section Re-treatment below).

In case of PASI score >0 at weeks 20 and/or 28 the subjects continue to receive guselkumab 100 mg q8w until week 60 (last administration of study treatment) with final study assessments at week 68 and final safety follow-up visit at week 72 (defined as study group **2c**).

Study Part 3: Week 68 through Week 220:

Subjects of group 2a and 2b with a PASI score <3 at week 68 enter Study Part 3 (in study groups **3a** and **3b**, respectively); they are withdrawn from the study medication and followed-up until week 220. Study visits of Study Part 3 are conducted every 12 weeks (ie, at weeks 80, 92, 104, 116, 128, 140, 152, 164, 176, 188, 200, and 212; \pm 14 days). In between the 12-weekly on-site visits, a telephone-visit 6 weeks (\pm 7 days) is done after each on-site visit (ie, telephone visits at weeks 74, 86, 98, 110, 122, 134, 146, 158, 170, 182, 194, and 206) to assess whether the subject notices a worsening of his/her psoriasis. If so, the subject must attend an on-site visit for efficacy assessment by the assessor as soon as possible but not later than 2 weeks after the phone call. For patients not starting re-treatment, the final visit takes place at week 220.

Re-treatment

Subjects losing control of disease, defined as PASI score >5 at any visit during Study Part 2 or 3 (ie, until week 220), enter the re-treatment-arms (**2d** or **3c**) with three guselkumab 100 mg administrations starting at that visit (= re-treatment-week 0, followed by administration at re-treatment-weeks 8 and 16).

If re-treatment is started at a visit which would usually not require all patient-reported outcomes needed at the first re-treatment visit, those patient-reported outcomes are obtained immediately after efficacy assessments (basis for re-treatment-decision) and prior to drug administration at that visit.

[figure not shown]
The final efficacy assessment for all subjects in the re-treatment arms takes place 24 weeks after loss of control, and study termination is 28 weeks after loss of control (final study visit/safety follow-up). At visit week 24 of the re-treatment, the investigator may continue actual treatment

with commercially available guselkumab (ie, not supplied by Sponsor) to maintain a q8w interval. Due to the half-life of guselkumab, it is recommended not to start a new therapy during safety follow-up period (ie, 12 weeks after last dose). If the investigator feels strongly that an additional therapy is needed, this should be discussed with the Sponsor before initiation of the new therapy.

Subjects with fluctuating disease (ie, PASI score 3 to 5) at the week 68 visit also get the opportunity to enter the re-treatment-arm (**3c**).

The last chance to start re-treatment is the visit week 220 (ie, final efficacy assessment at week 244 with final study visit/safety follow-up at week 248).

A schematic diagram of the study design is provided below.

2. STATISTICAL HYPOTHESES

This randomized, double-blind, parallel-group, multicenter phase 3b trial is designed to demonstrate that guselkumab 100 mg q16w treatment is non-inferior to guselkumab 100 mg q8w treatment in SRe as assessed by the proportion of subjects with an absolute PASI score <3 at week 68. A non-inferiority margin of 10% was chosen based on a minimally clinically meaningful difference. This margin was also used in CNTO1959PSO3009 (ECLIPSE) study and is therefore considered a valid approach for evaluating non-inferiority of a new treatment.

The null hypothesis H_0 and the alternative hypothesis H_A (*to be demonstrated in Study Part 2*) are formulated as follows:

- $H_0: P_T - P_S \leq -10\%$ ('inferiority')
- $H_A: P_T - P_S > -10\%$ ('non-inferiority'),

where P_T and P_S denote the proportions of subjects with an absolute PASI score <3 at week 68 in the guselkumab 100 mg q16w treatment arm (P_T = proportion test treatment) and the guselkumab 100 mg q8w treatment arm (P_S = proportion standard treatment).

3. SAMPLE SIZE DETERMINATION

The sample size estimation using the power approach was performed for the per-protocol analysis set as described below. No formal adjustment of the significance level was necessary.

When the sample size in each group is 112, a two-group large-sample normal approximation Wald Z-test of proportions with a one-sided 0.05 significance level will have 80% power to reject the null hypothesis that the guselkumab 100 mg q16w treatment is inferior to the guselkumab 100 mg q8w treatment (the difference in proportions, $P_{\text{guselkumab 100mg q16w}} - P_{\text{guselkumab 100mg q8w}}$, is $\leq -10\%$) in favor of the alternative hypothesis that the guselkumab 100 mg q16w treatment is non-inferior to the guselkumab 100 mg q8w treatment (the difference in proportions is $> -10\%$), assuming that the expected difference in proportions is 0 and the proportion in the guselkumab 100 mg q8w treatment group is 90% (nQuery Advisor® 7.0).

Considering the frequency of drop-out rates and protocol violations from past trials, it is assumed that a rate of about 20% randomized subjects will not be evaluable for the per-protocol analysis in Study Part 2. Therefore, 280 subjects (140 subjects per treatment group) are planned to be randomized in a ratio of 1:1 to meet the required sample size of 224 subjects (112 subjects per treatment group) for the per-protocol analysis.

Based on data from CNTO1959PSO3001 and CNTO1959PSO3002, it is anticipated that approximately 35% of enrolled subjects in Study Part 1 will be eligible for randomization at week 28 in Study Part 2. Thus, a total of 800 subjects should be enrolled in Study Part 1 to ensure that at least 280 subjects are eligible for randomization in Study Part 2. Accounting for a 10% drop-out rate of subjects ineligible for randomization at week 28 because of study discontinuation prior to week 28, it is therefore planned to enroll a total of 888 subjects in Study Part 1.

Note: Screenings and enrollments will be adjusted if necessary (without protocol amendment), to achieve 280 SRe at week 28. Ongoing subjects in Study Part 1 will continue to Part 2 if eligible, irrespective of whether or not 280 SRe are already randomized. Only screenings will be closed.

4. POPULATIONS (ANALYSIS SETS) FOR ANALYSIS OF STUDY PART 3

In Study Part 3 the following analysis sets will be defined for the efficacy and safety analyses.

4.1. All Enrolled Analysis Set

Not applicable for Study Part 3 (only applicable for Study Part 1). However, for Study Part 3 the number of 'Subjects starting Study Part 3 in groups 3a or 3b' will be reported and used for display of summary tables, if applicable.

Note: The All enrolled analysis set in Study Part 1 included all subjects who were enrolled and were scheduled to receive study agent.

4.2. Efficacy Analysis Set(s)

The exploratory efficacy analysis of the secondary endpoint variables will be performed for the Intent-to-treat analysis set (ITT). It was decided at the Dry Run Meeting for the Week 116 analysis that the PP analysis will not be performed.

4.2.1. Intent-to-Treat Analysis Set (ITT)

For all efficacy analyses to compare study groups **3a** and **3b** in Study Part 3, all subjects entering Study Part 3 (either group 3a or 3b) will be included in the Intent-to-treat analysis set (ITT).

Note1: Subjects entering study group 3c, ie, the re-treatment arm, will be evaluated separately. Analysis is not covered by the present SAP.

Note 2: In the current SAP template the term 'full analysis set' is used. In this SAP the term 'intent-to-treat analysis set' is used instead to match the Clinical Study Protocol. In terms of content, there is no difference between the two names.

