2. OBJECTIVES, ENDPOINTS, AND HYPOTHESIS

2.1. Objectives and Endpoints

2.1.1. Objectives

Primary objective

The primary objective of the study is to demonstrate that Super-Responders (SRe; defined as psoriasis subjects who receive on-label guselkumab treatment until week 20 and respond with a Psoriasis Area and Severity Index [PASI] score=0 at weeks 20 and 28) maintain control of disease until week 68 with prolonged treatment intervals of 16 weeks (100 mg q16w). *To be demonstrated in Study Part 2 (see Section 3.1 for study design).*

Secondary objectives

Secondary objectives are to evaluate

- whether subjects with short disease duration (≤ 2 years) show a more rapid and better guselkumab response compared to subjects with longer disease duration and whether subjects with shorter disease are more likely to maintain drug-free control of disease after guselkumab withdrawal. *To be evaluated in Study Parts 1, 2, and 3.*
- whether SRe with short disease duration and PASI=0 at week 116 (ie, remission for one year after withdrawal) will show sustained remission (ie, PASI=0) over two additional years compared to subjects with longer disease duration. *To be evaluated in Study Part 3.*
- whether SRe with short disease duration and PASI>0 to ≤ 5 at week 116 (ie, partial relapse for one year after withdrawal) will show continued loss of response or stabilization of disease worsening over two additional years compared to subjects with longer disease duration. *To be evaluated in Study Part 3.*
- whether different treatment intervals (weeks 28 to 60: guselkumab 100 mg q8w vs. guselkumab 100 mg q16w) affect the maintenance of drug-free control of disease after 68 weeks of guselkumab treatment. *To be evaluated in Study Part 3.*
- the safety and tolerability of guselkumab in subjects with moderate-to-severe plaque-type psoriasis.

Note: disease duration will be calculated from date at which first symptoms (plaque) were reported by subject to date of screening visit.

Exploratory objectives

The following objectives are to be explored in the mechanistic biomarker substudies:

- characterization of the immune cellular and molecular composition at baseline (week 0) and changes (quantitative and qualitative characterization) in the lesional skin of subjects during treatment with guselkumab as determined by fluorescence activated cell sorting (FACS)-based analysis. *To be explored in substudy 1*

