4. POPULATIONS (ANALYSIS SETS) FOR THE OVERALL SAFETY ANALYSIS

In the Overall safety analysis, the following analysis sets will be defined.

4.1. All Subjects Treated in Study Part 1

880 subjects started open-label guselkumab in Study Part 1 and received at least one dose (study group **1**). All 880 subjects are included in this analysis set to be evaluated for AEs in the study period from date of first dose (week 0) until the day before the date of the week 28 dose (start of randomized or open-label treatment within Study Part 2), or, in 58 subjects not starting Study Part 2, until the end of documentation.

4.2. All Subjects Treated in Study Part 2

From all 880 subjects who started open-label guselkumab in Study Part 1, 297 super-responders received randomized treatment in Study Part 2 (study groups **2a** and **2b**) and 525 non-super-responders continued open-label treatment (study group **2c**). So, 822 subjects are included in this analysis set and will be displayed separately to be evaluated for AEs in the study period from date

of the first verum dose (week 28 or week 36) until date of last verum dose (week 52 or week 60) in Study Part 2 plus 90 days (date of re-treatment and thereafter excluded, if at all).

4.3. All Subjects Randomized for Study Part 2

Among the 297 super-responders treated in Study Part 2 (study groups **2a** and **2b**), 148 were randomized to guselkumab q8w and 149 to guselkumab q16w. The 297 subjects included in this analysis set will be evaluated and displayed separately for AEs in the study period from date of randomization (week 28) until date of last verum dose (week 52 or week 60) in Part 2 plus 90 days (date of re-treatment and thereafter excluded, if at all).

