4.4. All Subjects with a Withdrawal Phase Longer than 90 Days

From all 273 subjects starting the Withdrawal phase after the week 68 visit (randomized subjects only, study groups **3a** and **3b**), those subjects will be selected who stay in the Withdrawal phase for more than 90 days after the last randomized verum dose of guselkumab. The subjects included in this analysis set will be evaluated for AEs in the study period starting from the 91st day after last verum dose in Study Part 2 until the day before re-treatment is started (if at all).

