4.2.5. Pharmacokinetics Analysis Set

The PK analysis and the definition of the PK analysis set is out of scope for this SAP.

5. STATISTICAL ANALYSES FOR STUDY PART 3

Description of planned statistical analyses in Study Part 3 will focus on the comparison of the two study groups 3a and 3b which are without administration of study agent in Study Part 3 (ie, group **3a**: randomized to guselkumab 100 mg q8w in Study Part 2 vs. group **3b**: randomized to guselkumab 100 mg q16w in Study Part 2). Inferential statistics (ie, exploratory p-values, confidence intervals, etc.) will be provided only for the week 116/164/220 data of endpoints in Study Part 3.

Note 1: Statistical analysis of Study Part 3 will also include analyses of study data recorded before week 68. Data of Study Parts 1 and 2 will be summarized by descriptive statistics only. No exploratory inferential statistics (ie, p-values, confidence intervals, etc.) will be provided for the data of Study Parts 1 and 2.

Note 2: Subjects of group 3a and 3b who start re-treatment with guselkumab within Study Part 3 (up to week 116) will be evaluated only up to the study visit R0 at which PASI >5 is shown. If PASI was ≥ 3 already at week 68 the subject will not be evaluated for Study Part 3 in the scope of this SAP; a separate SAP will describe the analysis of the re-treatment phase.

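### The Part 3 set called ITT holds only subjects who entered withdrawal (273 of 297), so the exploratory 3a-versus-3b tests are conditional comparisons that randomisation does not protect

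*SAP*

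**What the plan says.** - **Definition of the set.** Part 3 SAP, Section 4.2.1: "all subjects entering Study Part 3 (either group 3a or 3b) will be included in the Intent-to-treat analysis set (ITT". A note there says the ITT name replaces the template's full analysis set so as to agree with the protocol, and adds: "In terms of content, there is no difference between the two names".
- **Entry rule.** Part 3 SAP, Section 1.2: "Subjects of group 2a and 2b with a PASI score <3 at week 68 enter Study Part 3". Section 5, Note 2, says that if PASI was 3 or more "already at week 68 the subject will not be evaluated for Study Part 3 in the scope of this SAP".
- **Primary endpoint.** Part 3 SAP, Section 1.1.2: the proportion of subjects in groups 2a and 2b "who achieve an absolute PASI score <3 at week 68".
- **Tests.** Part 3 SAP, Section 5.4.3, compares 3a with 3b by a Wald Z-test with Mantel-Haenszel weights for disease duration, with 95% confidence intervals. Section 5.1 calls all of this exploratory, with nominal p-values. The per-protocol set (Section 4.2.2) is a subset of the ITT set, and Section 4.2 says it will not be analysed.
- **Protocol's use of the term.** Protocol Section 11.3 applies intent-to-treat to Part 2, where all subjects randomised at week 28 are analysed as randomised. For Part 3 it names subjects with at least one dose, analysed as treated, and does not call them ITT.
- **Objective.** Protocol Section 2.1.1 asks whether the two treatment intervals "affect the maintenance of drug-free control of disease after 68 weeks of guselkumab treatment".
- **Counts.** Overall safety SAP, Section 4.3: "148 were randomized to guselkumab q8w and 149 to guselkumab q16w". Section 4.4: "From all 273 subjects starting the Withdrawal phase after the week 68 visit". Section 4.5 lists nine subjects re-treated without a withdrawal phase: three before week 68 and six at week 68.

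**The concern.** Membership of the Part 3 set depends on something that happens after randomisation, and that something is the outcome on which the two arms were compared in Part 2. If the arms differ in how many subjects reach withdrawal, or in which ones, groups 3a and 3b are no longer the groups that randomisation created. A difference between them, or the absence of one, can then partly reflect who was selected.

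The label hides this. A p-value from an ITT set of a randomised trial will be read as a randomised comparison. The note in Section 4.2.1 justifies the name by agreement with the protocol, but the protocol has no ITT set for Part 3. The list of changes in Section 6.2 does not mention the set. No all-randomised analysis is planned for Part 3 that would let a reader see whether the selection matters.

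The retained-control endpoint shows the effect most clearly. It requires PASI <3 at every visit from week 68. On that wording the six subjects re-treated at week 68 with PASI 3 to 5 fail at its first visit, yet they are not in its denominator.

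**Working it through.** **1. Counts (overall safety SAP, Sections 4.2 to 4.5).** The document's own totals reproduce:
- 148 + 149 = 297 randomised and treated
- 297 + 525 = 822 treated in Part 2
- 227 + 9 = 236 re-treated

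The subjects outside the Part 3 set follow:
- 297 − 273 = 24, and 24/297 = 8.1%
- 3 + 6 = 9 of the 24 went straight to re-treatment
- 24 − 9 = 15 have no reason given in the documents

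**2. All-randomised difference when the planned analysis shows zero.** Let x of the 24 non-entrants be in the q16w arm. Let the same proportion p of entrants be in control in both arms, so the conditional difference is 0. Count non-entrants as not in drug-free control. Then

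D (q16w minus q8w) = p × [(149 − x)/149 − (148 − (24 − x))/148].

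**3. Values of p.**
- Week 220: 273 − 227 = 46 entrants did not start re-treatment, and 46/273 = 16.8%. This is an upper limit, because a re-treated subject is not in drug-free control and some of the 46 may have left or have PASI of 3 or more.
- Weeks 116 and 164: the documents give no control rate. I assume 30% and 50% as a range.

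**4. Results.** The split x is not stated anywhere, so the whole range is shown, in percentage points.

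| Non-entrants q8w / q16w | p = 16.8% | p = 30% | p = 50% |
|---|---|---|---|
| 24 / 0 | +2.7 | +4.9 | +8.1 |
| 16 / 8 | +0.9 | +1.6 | +2.7 |
| 12 / 12 | 0.0 | 0.0 | 0.0 |
| 8 / 16 | −0.9 | −1.6 | −2.7 |
| 0 / 24 | −2.7 | −4.8 | −8.1 |

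Example for the last row at 16.8%: 0.168 × (125/149 − 148/148) = 0.168 × (−0.161) = −0.027.

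**The case against.** The strongest reply is that the population is the right one for the question. Protocol Section 2.1.2 defines 3a and 3b as subjects withdrawn at week 68 and attaches the retained-control endpoint to those groups. The interval objective concerns drug-free control after week 68, and someone re-treated at or before week 68 has none to maintain. This stands: the conditional analysis should stay, and an all-randomised table answers a broader question.

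Three further points also stand:
- The selection is disclosed in Part 3 SAP Section 4.2.1, Note 1, and Section 5, Note 2. Section 5.2 reports entrants by study group, so the number of non-entrants per arm can be derived by subtracting from 148 and 149. The reasons cannot.
- Part 3 is exploratory throughout, and no confirmatory claim rests on this set.
- Sections 5.5.1.1 and 5.7.2 provide for a missed week 68 visit, so entry may not rest on a recorded PASI <3 in every case.

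A reader might infer that failures under q16w before week 68 escape being counted. They do not. Protocol Section 11.11 counts PASI of 3 or more, earlier discontinuation and a missed week 68 evaluation as non-response in the Part 2 primary analysis. A reader might also infer that the Part 3 comparison flatters q16w. The documents do not give the arm split, and reverse splits give the opposite sign.

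The objection does not rescue the label, and it does not supply a comparison protected by randomisation.

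**Conclusion.** The point holds as one of labelling and sensitivity within the exploratory Part 3. The set is not intent-to-treat in the sense in which the protocol uses the term, and the 3a-versus-3b tests are conditional on entering withdrawal.

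The direction of any distortion is unknown. Its size ranges from about 0 with a balanced split to about 2.7 points either way at week 220 if all 24 are in one arm. At earlier visits the same extreme gives about 4.8 to 8.1 points if 30% to 50% of entrants are in control. Those figures rest on equal control among entrants, on counting non-entrants as not in control, and on the assumed rates before week 220. The extremes are bounds and not forecasts.

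Stronger readings are not supported. An effect of 8 points at week 220 is ruled out by the 16.8% ceiling under these assumptions. The 24 cannot all be called PASI failures, since only nine have a recorded reason. The figures 297 and 273 come from the overall safety SAP; the Part 3 SAP states no number of its own. The confirmatory Part 2 result is untouched.

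**What to change.** 1. Rename the set, for example as the withdrawal analysis set, and drop the statement that its name matches the protocol.
2. Report the subjects who did not enter withdrawal by randomised arm, with reasons.
3. State beside the tests that 3a versus 3b is conditional on entering withdrawal and is not protected by randomisation.
4. For PASI 0, ≤1 and <3 and for retained control at weeks 116, 164 and 220, add a sensitivity analysis of all randomised subjects by randomised group. Count non-entrants as not in drug-free control, use the existing non-responder rule (Part 3 SAP, Section 5.1.8) for the rest, and show it next to the conditional result.

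The cost is a few extra tables and no new data collection. The downside is that the added analysis answers a broader question than drug-free maintenance, which is why both results should be shown together.
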